8.2. Secondary Efficacy Endpoints

8.2.1. Key Secondary Endpoints

If the primary analysis of primary endpoint leads to rejection of the null hypotheses, key secondary endpoints will be tested by using the Hochberg approach (Hochberg Y. 1988) to show superiority of each concentration for which superiority vs. vehicle has been proven in the primary analysis.

Hochberg approach will be achieved by the following procedure:

1. Put all p values in descending order and assign ranks to those p values according to their ranks.
2. Calculate each individual adjusted p-value using Hochberg approach.
3. Compare the adjusted p-values from Step 2 with the alpha level for the comparison vs. vehicle for which superiority has been shown for the primary endpoint.
4. All the tests corresponding to those p values ranking ahead of the p value selected in Step 3, including the test corresponding to the p value selected in Step 3, will be considered as significant. The null hypothesis will be rejected.

The Hochberg approach will be implemented by SAS PROC MULTTEST procedure and HOCHBERG option.

This hierarchical test strategy protects the family-wise false positive error rate at the overall one-sided 0.0125 level for each concentration vs. vehicle. With 92 patients evaluable per treatment group, the study would have approximately a power of 67% to test the endpoint with the smallest p-value in the worst-case scenario where the first 2 endpoints tested are not statistically significant (i.e. with an adjusted alpha level of 0.00417).

In case of not rejection of the null hypothesis for primary endpoint (or for the concentration for which the superiority is not shown), the above testing strategy for key secondary endpoints will not be performed. Instead, independently of results on primary endpoint, descriptive in nature analyses will be performed on all key secondary endpoints at each available timepoint by means of descriptive statistics.

Descriptive statistics for key secondary endpoints assessments at each visit will be presented based on observed data and data after applying hypothetical strategy.

8.2.1.1. Proportion of patients improving to Schirmer-I test without anesthesia ≥ 10 mm/5min in the Study Eye at week 4

Missing data will be imputed by using a multiple imputation with copy-reference approach (see [Section 8.1.1](#)). For each imputed dataset, the change from baseline at Week 4 is derived. Patients with change from baseline at Week 4 ≥ 10 mm/5min will be considered as having improvement while patients with change from baseline at Week 4 < 10 mm/5mins will be considered as not having improvement. 95% CI on proportion of patients having improvement will be implemented by using Clopper Pearson method.

The derived binary variable described in the previous step will then be used in a logistic model as dependent variable; treatment (3 levels: rhNGF \blacksquare mcg/mL, rhNGF \blacksquare mcg/mL, and vehicle) and baseline Schirmer-I scores in the Study Eye as covariates.

Based on this modeling, the estimated proportions and corresponding two-sided 95% CI will be provided for each treatment arm; the estimated mean proportion differences, two-sided 95% CI, and corresponding one-sided p-value will be provided for each IMP group versus vehicle at Week 4.

8.2.1.2. Mean change from baseline in Schirmer-I score without anesthesia in the Study Eye at Week 4

The MI procedure described in [Section 8.2.1.1](#) will be applied to impute missing Schirmer-I scores at Week 4. Change from baseline at Week 4 will be fitted in the ANCOVA model with change from baseline at Week 4 as dependent variable, treatment (3 levels: rhNGF \blacksquare mcg/mL, rhNGF \blacksquare mcg/mL, and vehicle) and baseline Schirmer-I scores in the Study Eye as covariates.

Based on this modeling, a point estimate (the adjusted estimated treatment effect), associate SE, two-sided 95% CI, and corresponding one-sided p-value will be provided for each treatment group; a point estimate (the adjusted estimated treatment difference), associate SE, two-sided 95% CI, and corresponding one-sided p-value will be provided for each least squares (LS) mean treatment difference versus placebo at Week 4.

8.2.1.3. Mean change from baseline in total corneal fluorescein staining (NEI scale) in the Study Eye as assessed by the investigator at week 4

Corneal fluorescein staining has 5 zones and each zone has a score range of 0-3. The total score is determined by simply adding up the scores of the 5 individual zones. The range of total corneal fluorescein staining in NEI scale is 0-15. If any of the 5 individual zones has a missing score, the total score would be missing.

The analysis method described in [Section 8.2.1.2](#) will be repeated with change from baseline at Week 4 of total corneal fluorescein staining (NEI scale) in the Study Eye as dependent variable.

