3.2.2 Key Secondary Estimands

Key secondary objective #1

The estimand for the key secondary objective #1 is defined as follows:

- Treatment: 4 weeks of TID administration of rhNGF new formulation (two concentrations and vehicle).
- Population: Male and female patients aged ≥ 18 years with dry eye. Full Analysis Set.
- Variable: proportion of patients improving to Schirmer-I test without anesthesia ≥ 10 mm/5min in the Study Eye at week 4 (V4).
- Intercurrent events (ICEs) and strategies to handle them:
 - Treatment discontinuation: a treatment policy strategy will be applied where all the observed values will be used regardless of the occurrence of the ICEs. Missing data due to any reason will be handled by using a multiple imputation with a copy-

- reference approach (see § 10.6.3 for further details).
- Use of a prohibited medication, as listed in § 6.6.1, in the week before any assessment of Schirmer-I score: a hypothetical strategy will be applied where any data collected in the week after the occurrence of the ICE will be discarded. Missing data for Schirmer-I score will be imputed by using a multiple imputation with copy-reference approach (see § 10.6.3 for further details), then the proportion of subjects with an improvement ≥ 10 mm/5min in the Study Eye will be derived.
 - Population-level summary: difference in proportion of patients improving to Schirmer-I test without anesthesia ≥ 10 mm/5min in the Study Eye at week 4 (V4) between each concentration group of IMP (groups IMP1 and IMP2) and the vehicle group as derived by a logistic model defined in § 10.6.3.

In summary, the estimand for the key secondary objective #1 is defined as the difference in proportion of patients improving to Schirmer-I test without anesthesia ≥ 10 mm/5min in the Study Eye at week 4 (V4) between treatments in the targeted patient population regardless of study treatment discontinuation and had prohibited medications not been available to subjects in the week before any study evaluation.

Key secondary objective #2

The estimand for the key secondary objective #2 is defined as follows:

- Treatment: 4 weeks of TID administration of rhNGF new formulation (two concentrations and vehicle).
- Population: Male and female patients aged ≥ 18 years with dry eye. Full Analysis Set.
- Variable: mean change from baseline in Schirmer-I score without anesthesia in the Study Eye at week 4 (V4).
- Intercurrent events (ICEs) and strategies to handle them:

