5.1 INCLUSION CRITERIA

- 1) Male or female aged ≥ 18 years of any race/ethnicity and eye color.
- 2) A diagnosis of dry eye disease at least 6 months before enrollment (current use or recommended use of artificial tears for the treatment of dry eye).
- 3) Moderate-to-severe dry eye characterized by the following clinical features:

- a) Symptoms Assessment in Dry Eye (SANDE) questionnaire global score ≥ 50 , and
 - b) Schirmer-I test without anesthesia > 2 mm and < 10 mm/5 minutes, and
 - c) Total corneal fluorescein staining grade ≥ 3 (NEI scale) and/or total conjunctival lissamine green staining score ≥ 3 assessed by the National Eye Institute (NEI) grading system, and
 - d) Fluorescein Tear Film Break-Up Time (fTBUT) < 10 seconds. The same eye must have fulfilled all the above criteria.
- 4) Best corrected distance visual acuity (BCDVA) score on ETDRS chart of ≥ 0.1 decimal units (≤ 1.0 logMAR) in each eye at the time of study enrollment
 - 5) Negative pregnancy test in females of childbearing potential.
 - 6) Only patients who satisfy all informed consent requirements will be included in the study; the patient and/or his/her legal representative must have read, signed, and dated the informed consent document before any study-related procedures are performed; the informed consent form signed by patients and/or legal representatives must have been approved by the IRB for the current study.
 - 7) Have the ability and willingness to comply with study procedures.

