3.2. Study Endpoints

Objectives	Endpoints
Primary Objective 
 To evaluate the efficacy of CCI mcg/mL and CCI mcg/mL concentrations of the new formulation of rhNGF ophthalmic solution versus vehicle, in order to demonstrate superiority of at least one of the concentrations over vehicle in the improvement of ocular symptoms of dry eye in patients with dry eye disease (DED). 	Primary Efficacy Endpoint 
 Mean change from baseline to Week 8 in symptoms of dry eye assessed by SANDE Global Score [Time Frame: week 8 (V5)]

Objectives	Endpoints
Key Secondary Objectives	Key Secondary Efficacy Endpoints

 To evaluate the efficacy of the new formulation of rhNGF ophthalmic solution in increasing the number of patients with improved reflex tear production as compared to vehicle at week 4 	
 Proportion of patients improving to Schirmer-I test without anesthesia ≥ 10 mm/5min in the Study Eye [Time Frame: at week 4 (V4)]

 To evaluate the efficacy of the new formulation of rhNGF ophthalmic solution in improving reflex tear production as compared to vehicle at week 4 	
 Mean change from baseline in Schirmer-I score without anesthesia in the Study Eye [Time frame: at week 4 (V4)]

 To evaluate the efficacy of the new formulation of rhNGF ophthalmic solution in improving ocular surface integrity (corneal epitheliopathy) as compared to vehicle at week 4 	
 Mean change from baseline in total CCI [redacted] in the Study Eye as assessed by the investigator [Time Frame: at week 4 (V4)]
Secondary Objectives	Secondary CCI [redacted] (*) Efficacy Endpoints

 To evaluate the efficacy of the new formulation of rhNGF ophthalmic solution in improving reflex tear production as compared to vehicle at week 8 	
 Mean change from baseline in Schirmer-I score without anesthesia in the Study Eye [Time frame: at week 8 (V5)] Proportion of patients improving to Schirmer-I test without anesthesia ≥ 10 mm/5min in the Study Eye [Time Frame: at week 8 (V5)]

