3.3.2. Key Secondary Estimands

Key secondary objective #1

The estimand for the key secondary objective #1 is defined as follows:

- Treatment: 4 weeks of CCI administration of rhNGF new formulation (CCI and vehicle).
- Population: Male and female patients aged ≥ 18 years with dry eye. Full Analysis Set.
- Variable: proportion of patients improving to Schirmer-I test without anesthesia ≥ 10 mm/5min in the Study Eye at week 4 (V4).
- ICEs and strategies to handle them:
 - Treatment discontinuation (only IMP): a treatment policy strategy will be applied where all the observed values will be used regardless of the occurrence of the ICEs. Missing data due to any reason will be handled by using a multiple imputation with a copy-reference approach (see [Section 8.2.1](#) for further details).
 - Use of a prohibited medication, in the week before any assessment of Schirmer-I score: a hypothetical strategy will be applied where any data collected in the week after the occurrence of the ICE will be discarded. Missing data for Schirmer-I score will be imputed by using a multiple imputation with copy-reference approach (see [Section 8.2.1](#) for further details), then the proportion of patients with an improvement ≥ 10 mm/5min in the Study Eye will be derived.
- Population-level summary: difference in proportion of patients improving to Schirmer-I test without anesthesia ≥ 10 mm/5min in the Study Eye at week 4 (V4) between each concentration group of IMP (groups IMP1 and IMP2) and the vehicle group as derived by a logistic model defined in [Section 8.2.1](#).

In summary, the estimand for the key secondary objective #1 is defined as the difference in proportion of patients improving to Schirmer-I test without anesthesia ≥ 10 mm/5min in the Study Eye at week 4 (V4) between treatments in the targeted patient population regardless of study treatment discontinuation and had prohibited medications not been available to patients in the week before any study evaluation.

Key secondary objective #2

The estimand for the key secondary objective #2 is defined as follows:

- Treatment: 4 weeks of CCI administration of rhNGF new formulation (CCI

- CCI and vehicle).
- Population: Male and female patients aged ≥ 18 years with dry eye. Full Analysis Set.
- Variable: mean change from baseline in Schirmer-I score without anesthesia in the Study Eye at week 4 (V4).
- ICEs and strategies to handle them:

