8.2.2.1. Secondary Endpoints

Although the method of analysis for the secondary endpoints is the same as the one established for the key secondary endpoints and that for SANDE at week 4 is the same of the one used for the primary endpoint, the results of the analyses on the secondary endpoints are to be interpreted as descriptive in nature, since no adjustment of the overall alpha level has been applied for taking care of these endpoints.

Mean change from baseline in Schirmer-I score without anesthesia in the Study Eye at Week 8

Actual values and changes from baseline to Week 8 in Schirmer-I score without anesthesia will be summarized by means of descriptive statistics for the Study Eye. The comparisons between each active treatment and vehicle at week 8 will be performed using the same ANCOVA model and imputation strategy described in [Section 8.2.1.2](#) for the comparisons at week 4; consequently, the point estimates, corresponding 95% CIs and p-values described in that section will be provided also for the week 8 timepoint.

Proportion of patients improving to Schirmer-I test without anesthesia ≥ 10 mm/5min in the Study Eye at week 8

Patients will be categorized into two levels: result ≥ 10 mm/5min in the Study Eye and result < 10 mm/5min in the Study Eye. The derived binary variable will then be summarized at Week 8 in a frequency table.

The comparisons between each active treatment and vehicle at week 8 will be performed using the same logistic model and imputation strategy described in section 8.2.1.1 for the comparisons at week 4; consequently, the point estimates, corresponding 95% CIs and p-values described in that section will be provided also for the week 8 timepoint.

Mean change from baseline in fluorescein tear break-up time (fTBUT) in Study Eye at weeks 4 and 8

The fTBUT will be measured twice during the first minute after the instillation of the fluorescein. If the 2 readings differ by more than 2 seconds, then a third reading is taken. The fTBUT value (in seconds) will be set to the average of the 2 or 3 measurements.

Actual values and changes from baseline to Week 4 and Week 8 in fTBUT will be summarized by means of descriptive statistics for the Study Eye.

The ANCOVA model described in [Section 8.2.1.2](#) and the imputation strategy described in [Section 8.1.1](#) will be applied to fTBUT in Study Eye at Week 4 and Week 8 separately.

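### SAP 8.2.1.1 scores key secondary endpoint 1 as a Schirmer-I rise of at least 10 mm, but the endpoint is reaching a value of at least 10 mm

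*SAP*

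**What the plan says.** **Endpoint and estimand.** SAP 3.2 lists the first key secondary endpoint as "Proportion of patients improving to Schirmer-I test without anesthesia" at or above 10 mm/5 min, Study Eye, Week 4. The estimand variable in Protocol 3.2.2 is the "proportion of patients improving to Schirmer-I test without anesthesia ≥ 10 mm/5min in the Study Eye at week 4 (V4"). SAP 3.3.2 states the same variable. The population-level summary and closing summary of that estimand repeat it in both documents, and so does the heading of SAP 8.2.1.1.

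**Derivation at Week 4.** SAP 8.2.1.1 imputes the score, derives the change from baseline and then says: "Patients with change from baseline at Week 4 ≥ 10 mm/5min will be considered as having improvement". A change below 10 mm is classed as no improvement. This binary variable goes into the logistic model.

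**Derivation at Week 8.** For the same endpoint one visit later, SAP 8.2.2.1 says: "Patients will be categorized into two levels: result ≥ 10 mm/5min in the Study Eye". It then refers back to 8.2.1.1 for the model and the imputation.

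**Entry range.** Protocol 5.1, criterion 3b: "Schirmer-I test without anesthesia > 2 mm and < 10 mm/5 minutes".

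**Looser wording.** In the handling of prohibited medication, SAP 3.3.2 imputes the score, "then the proportion of patients with an improvement" of 10 mm or more. Protocol 3.2.2 and 10.6.4 use similar words.

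**The concern.** Reaching 10 mm and rising by 10 mm are different outcomes when every patient starts above zero. A patient who goes from 4 to 12 mm has reached the target (12 ≥ 10) but is a failure under the Week 4 rule (12 − 4 = 8).

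The endpoint is one of three in the multiplicity-controlled key secondary family. As written, its p-value would belong to an outcome that neither document's endpoint list or estimand variable describes. Hochberg is a step-up procedure with one-sided thresholds 0.0125, 0.0125/2 = 0.00625 and 0.0125/3 = 0.00417. If this endpoint has the largest p-value and misses 0.0125, the other two face the tighter thresholds. A miscoded responder can therefore change the conclusions on mean Schirmer-I change and corneal staining. Week 4 and Week 8 rates would also appear under one name with two meanings.

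**Working it through.** **1. The plan's own figure.** SAP 8.2.1 and Protocol 10.6.4 state about 67% power for the key secondary family at one-sided 0.00417 with 92 per group.

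- Inputs (Protocol 10.1): mean changes −28.2 and −17.4, SDs 26.36 and 20.29, so the difference is 10.8.
- SE = √[(26.36² + 20.29²)/92] = √(1106.5/92) = 3.47, and 10.8/3.47 = 3.11.
- Welch t power: 67.2% at 0.00417 and 80.2% at 0.0125.

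Both stated figures reproduce, but from the SANDE inputs. No Schirmer-I rate enters them, so the 67% says nothing about power for this binary endpoint under either rule.

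**2. What each rule requires.** Let B be baseline and Y the Week 4 value.

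| Rule | Condition | Whole-mm baseline 3 to 9 |
|---|---|---|
| Endpoint (level) | Y ≥ 10 | rise of 10 − B = 7 down to 1 mm |
| SAP 8.2.1.1 (change) | Y ≥ B + 10 | Week 4 value of 13 to 19 mm |

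Since B ≥ 0, Y ≥ B + 10 implies Y ≥ 10. The change responders are a subset of the level responders. This needs no assumption about effect size.

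**3. How much rarer (illustration only).** The documents give no Schirmer-I mean change, SD or response rate. Assumed: baseline uniform on 3 to 9 mm, normal change, values rounded and limited to 0–35 mm. Over mean changes of 0 to 5 mm and SDs of 4, 6 and 8 mm, the level rule gives 22% to 63% responders and the change rule 1% to 29%. The ratio runs from 24.5 (mean 0, SD 4) to 2.0 (mean 5, SD 8).

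**4. Power (illustration only).** 92 per arm, one-sided 0.0125, with

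power = Φ{[p_A − p_V − z√(2p̄(1−p̄)/n)] / √[(p_A(1−p_A) + p_V(1−p_V))/n]}, z = 2.241.

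| Mean change, vehicle / active | SD | Level rule | Power | Change rule | Power |
|---|---|---|---|---|---|
| +1 / +3 | 4 | 28.9% vs 45.6% | 54% | 1.7% vs 5.2% | 17% |
| +1 / +4 | 4 | 28.9% vs 54.5% | 91% | 1.7% vs 8.5% | 44% |
| +2 / +5 | 4 | 37.0% vs 63.1% | 91% | 3.1% vs 13.0% | 60% |
| +1 / +3 | 6 | 34.6% vs 46.9% | 29% | 7.8% vs 14.0% | 18% |
| +1 / +4 | 6 | 34.7% vs 53.2% | 61% | 7.9% vs 18.0% | 42% |
| +2 / +5 | 6 | 40.6% vs 59.3% | 62% | 10.6% vs 22.7% | 49% |
| +1 / +3 | 8 | 38.2% vs 47.6% | 17% | 14.4% vs 20.8% | 13% |
| +1 / +4 | 8 | 38.1% vs 52.5% | 39% | 14.4% vs 24.6% | 31% |
| +2 / +5 | 8 | 42.8% vs 57.3% | 39% | 17.4% vs 28.7% | 33% |

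The change rule is weaker in all nine scenarios, by 4 to 47 points. This is an unadjusted two-proportion approximation to the planned logistic model. It is rough at the lowest rates: 1.7% of 92 is fewer than two vehicle responders.

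**The case against.** The best counter-argument is that the SAP author did not invent the change rule. Protocol 3.2.2 and 10.6.4 and SAP 3.3.2 each describe an improvement of 10 mm or more, and SAP 8.2.1.1 is a natural reading of that phrase. The ambiguity therefore runs through both documents, and the sponsor's intent has to be inferred. This stands as an explanation of the error. It does not outweigh the endpoint lists, the estimand variable and summaries, the section's own heading and the Week 8 rule, which all describe the level. Protocol 10.6.4 also names change and improvement as two separate derived quantities.

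Three further points have some force:

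- The clause in SAP section 1 giving the SAP precedence does not settle the matter, because here the SAP disagrees with itself. But 8.2.1.1 holds the only operative Week 4 derivation, so that is what would be programmed.
- The harm has limits. The endpoint is tested only for a concentration that has already won on SANDE, and the primary analysis is untouched. A pre-specified change rule does not inflate type I error for its own hypothesis, and Week 8 is declared descriptive. Being listed first carries no weight under Hochberg.
- The entry range is guaranteed only for an eye that qualifies, and the choice of Study Eye presumes that both do. If the lower-Schirmer eye were used without qualifying, its baseline could be 2 mm or less. The subset argument would still hold, with the two rules coinciding only at a baseline of zero.

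**Conclusion.** The concern holds. The operative Week 4 rule tests a different outcome from the stated endpoint and estimand, and SAP section 11, which lists changes to the planned analysis, does not mention it. That the coded outcome is a subset follows from baseline being non-negative. That it is much rarer is well supported but not fixed by the documents: 2.0 to 24.5 times fewer responders over the assumed range, so half or more of the patients who meet the endpoint would be counted as failures in every scenario tried. The power loss depends heavily on the assumed SD, from large at SD 4 to a few points at SD 8. Because a multiplicity-controlled endpoint is coded as another outcome, this must be corrected before the analysis is run.

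**What to change.** In SAP 8.2.1.1, define the Week 4 responder, after imputation of the continuous score, as a Study Eye Schirmer-I result of at least 10 mm/5 min (yes/no). This matches the Week 8 rule in 8.2.2.1. Change from baseline stays where it belongs, in key secondary endpoint 2.

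In SAP 3.3.2, and in Protocol 3.2.2 and 10.6.4, replace the phrase about an improvement of 10 mm or more with a result of 10 mm or more. If the sponsor did intend a 10 mm rise, then the endpoint, the estimand and the Week 8 rule must be rewritten instead and the change declared.

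The cost in the SAP is one derivation sentence, one wording correction and one line of code before database lock. The protocol sentences need a protocol change, or at least a clarification recorded in SAP section 11. If the database is already locked, the correction should be justified in the clinical study report.

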8.2.2. Secondary \blacksquare Analyses

The secondary endpoints will be analyzed following the indications provided in the protocol for the key secondary endpoints, but actual observed data will be used regardless the onset of Intercurrent events. \blacksquare

